### **6.6.1.2 Hepatic Impairment**

Acalabrutinib clinical safety has not been evaluated in patients with severe hepatic impairment. If acalabrutinib is administered to participants with hepatic impairment, monitor participants carefully for AEs and follow the recommended dose modifications in Table 7.

The PK acalabrutinib in participants with hepatic impairment has been studied. Briefly, the AUC of acalabrutinib increased 1.9-fold in participants with mild hepatic impairment (Child-Pugh class A), 1.5-fold in participants with moderate hepatic impairment (Child-Pugh class B), and 5.3-fold in participants with severe hepatic impairment (Child-Pugh class C) compared with participants with normal liver function. No clinically relevant PK difference in ACP5862 was observed in participants with severe hepatic impairment (Child-Pugh class C) compared with participants with normal liver function. No clinically relevant PK differences in acalabrutinib and ACP5862 were observed in participants with mild or moderate hepatic impairment (TBL  $\leq$  ULN and AST  $>$  ULN, or TBL  $>$  ULN and any AST) relative to participants with normal hepatic function (TBL and AST within ULN).

## **6.7 Intervention After the End of the Study**

There is no intervention following the end of the study.

## **7 DISCONTINUATION OF STUDY INTERVENTION AND PARTICIPANT DISCONTINUATION/WITHDRAWAL**

### **7.1 Discontinuation of Study Intervention**

Participants may discontinue study intervention for the following reasons:

- Positive HBsAg, HBV-DNA, or HCV-RNA test result after the first dose
- Completed treatment
- Pregnancy
- Adverse event
- Investigator's decision
- Participant withdrawal of consent from study
- Decision by the Sponsor to terminate the study
- Lost to follow-up
- Death
- Other

Note that discontinuation from study intervention is NOT the same thing as a withdrawal from the study.

A participant that decides to discontinue study intervention will always be asked about the reason(s) and the presence of any AEs. The date of last intake of study intervention should be documented in the eCRF.

Participants should have follow-up assessments for safety 28 ( $\pm$  3) days after the last dose of acalabrutinib (whether due to discontinuation or completion of dosing) (see Table 1).

Telemedicine is recommended for capturing AEs and concomitant medications. Safety laboratory tests can be done at the hospital or a local laboratory provided the results are ultimately captured in the clinical database for the study.

### **7.2 Participant Withdrawal from the Study**

A participant may withdraw from the study at any time at his/her own request or may be withdrawn at any time at the discretion of the Investigator for safety, behavioral, compliance, or administrative reasons. This is expected to be uncommon.

Participants with a positive HBsAg, HBV-DNA, or HCV-RNA test result after the first dose will be withdrawn from the study.

A participant who considers withdrawing from the study must be informed by the Investigator about modified follow-up options (eg, telephone contact, a contact with a relative or treating physician, or information from medical records).

At the time of withdrawal from the study, if possible, an Early Study Intervention Discontinuation visit should be conducted. If this visit occurs prior to Day 14, the Day 14 schedule of assessments should be followed, and if it occurs between Days 14 and 28, the Day 28 schedule of assessments should be followed. See SoA (Table 1) for data to be collected on these days and for follow-up and any further evaluations that need to be completed. The participant will discontinue the study intervention and be withdrawn from the study at that time.

If the participant withdraws consent for disclosure of future information, the Sponsor may retain and continue to use any data collected before such a withdrawal of consent.

If a participant withdraws from the study, it should be confirmed if he/she is still agreeing for existing samples to be used consistent with the original consent. If he/she requests withdrawal of consent for use of samples, destruction of any samples taken and not tested should be carried in line with what was stated in the informed consent and local regulation. The Investigator must document the decision on use of existing samples in the site study records and inform the Global Study Team.

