### **4.4 End of Study Definition**

The end of the study is defined as the last expected visit/contact of the last participant in the study.

A participant is considered to have completed the study if he/she has completed his/her last scheduled procedure shown in the SoA (Table 1).

All participants who discontinue study intervention for any reason other than withdrawal of consent, loss to follow-up, or death will have a safety follow-up assessment 28 ( $\pm$  3) days after the last dose of acalabrutinib, as outlined in Section 1.3.

The study may be stopped if, in the judgment of the Sponsor, participants are placed at undue risk because of clinically significant findings.

Refer to Appendix A 5 for guidelines for the dissemination of study results.

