#### 8.2.5.1.1 Hepatitis Serology Guidelines

If feasible, hepatitis serology data should be obtained prior to administration of the first dose. However, if not feasible, sites should proceed as described below.

Participants must not meet Exclusion Criterion 9 (see Section 5.2):

- Known active hepatitis B or C infection as determined by active treatment
- Medical history or any routine clinical or laboratory evidence, that in the judgement of the Investigator, suggests chronic or active viral hepatitis.

Blood samples for all HBV and HCV serology tests, and for both HBV and HCV PCR tests must then be collected **before** administration of the first dose.

- If results become available before administration of the first dose, participants with positive HBsAg, HBV-DNA, or HCV-RNA test results will be excluded and should be treated per institutional guidelines.

- Participants who are anti-HBc positive and who are HBsAg negative will need to have a negative or undetectable hepatitis B viral load (HBV-DNA) by quantitative PCR result.
- Participants who are HCV antibody positive will need to have a negative PCR.
- If results are not available at the time of first dose administration, participants can be started on acalabrutinib. If any of the HBsAg, HBV-DNA, or HCV-RNA test results are positive after the first dose, the following must occur:
  - Discontinue further treatment with acalabrutinib.
  - Withdraw the participant from the study.
  - Modify BSC as clinically indicated per Investigator judgement.
  - Initiate a monitoring and therapeutic plan for HBV/HCV infection according to institutional guidelines and Investigator judgement.

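### Sections 7.2 and 8.2.5.1.1 withdraw hepatitis-positive participants from the study, while Sections 4.4, 7.1 and 8.3.1 and Table 1 require safety follow-up to 28 (±3) days after the last dose with no hepatitis exception

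*Protocol*

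**What the plan says.** Two places in the protocol order withdrawal from the study.

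- Section 7.2: "Participants with a positive HBsAg, HBV-DNA, or HCV-RNA test result after the first dose will be withdrawn from the study". It asks for an early discontinuation visit, but only where one can be held, and adds: "The participant will discontinue the study intervention and be withdrawn from the study at that time".
- Section 8.2.5.1.1 makes two separate mandatory steps of it: stop acalabrutinib, and "Withdraw the participant from the study". Hepatitis monitoring afterwards is left to institutional guidelines and the investigator's judgement, with no mention of study data capture.

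Four places require follow-up and make no exception for hepatitis.

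- Section 4.4: "All participants who discontinue study intervention for any reason other than withdrawal of consent, loss to follow-up, or death will have a safety follow-up assessment". The interval set for it is four weeks from the final dose, give or take 3 days.
- Section 7.1 lists among the reasons for stopping drug "Positive HBsAg, HBV-DNA, or HCV-RNA test result after the first dose". Its own safety follow-up has the same interval, counted in "days after the last dose of acalabrutinib (whether due to discontinuation or completion of dosing").
- Table 1, footnote g, applies the same follow-up to all participants.
- Section 8.3.1 collects adverse events from consent to 28 (±3) days after the last dose.

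**The concern.** The two groups of instructions cannot both be followed as written. A participant whose positive result arrives after dosing has stopped drug for a reason outside Section 4.4's three exceptions, so the safety follow-up is owed. The same participant has been withdrawn from the study, which ordinarily ends study procedures. Different sites could act differently.

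Safety is a primary objective in a study of about 20 people. Participants withdrawn by this rule have been dosed, so under Table 9 they belong to the Safety Analysis Set and the Efficacy Evaluable Set. They need not have withdrawn consent. Any data gap would therefore come from the protocol's own instruction. It would also sit awkwardly with the Amendment 2 rationale, which accepts dosing before results partly because hepatitis events can be monitored.

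**Working it through.** The plan states no figure on this point, so there is nothing to reproduce. The check is a side-by-side reading, a timeline and a rough count.

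**1. Does any text settle the conflict?** Section 4.4 names withdrawal of consent, loss to follow-up and death. Withdrawal by rule for a hepatitis result is none of these. Section 7.2 refers the reader to Table 1 for data to collect and for follow-up, but does not say that the 28-day assessment survives this withdrawal. The modified follow-up options in Section 7.2 are for a participant who is considering withdrawal, not for one removed by rule. No sentence says either that follow-up continues or that it stops.

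**2. What is at stake in time?** The safety assessment falls on last-dose day + 28, with a window of +25 to +31.

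- Last dose Day 2: Day 30 (27 to 33).
- Last dose Day 5: Day 33 (30 to 36).
- Last dose Day 14: Day 42 (39 to 45).

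If withdrawal takes effect when the result arrives and drug is stopped, in-study follow-up after the last dose is close to 0 days instead of 28.

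**3. Can the early visit replace the missing assessments?** Only partly. Before Day 14 it uses the Day 14 assessments, and between Days 14 and 28 the Day 28 assessments. Section 9.4.4.1, however, counts only survival and respiratory status on Days 14 and 28 themselves. A visit on Day 5 gives neither.

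**4. How would the gap enter the analysis?** Section 9.4.1 applies no imputation for efficacy and uses reduced denominators for safety. Section 9.4.4.3 censors a participant who drops out without improvement. With 20 dosed, one participant is 1/20 = 5% of the set. If one Day 28 status is unknown and x of the others are alive and free of respiratory failure, the proportion lies between x/20 and (x + 1)/20, a range of 5 percentage points. That is a bound on uncertainty, not an expected shift in the estimate.

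**5. How many participants?** The protocol gives no rate of positive results after dosing. Assume a rate p of 1% to 5% applied to all 20.

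- Expected number = 20 × p: 20 × 0.01 = 0.2; 20 × 0.05 = 1.0.
- Chance of at least one = 1 − (1 − p)^20: 1 − 0.99^20 = 18%; 1 − 0.95^20 = 64%.

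Both overstate the problem for a given p. Exclusion Criterion 9 removes known or suspected hepatitis, and Section 8.2.5.1.1 excludes positives whose results return before dosing.

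**6. What should not be counted?** If drug stops before PK Visit 2, PK evaluability is lost because of the stopping rule, which is not at issue here.

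**The case against.** The best defence is that nothing cancels the safety assessment. Sections 4.4, 7.1 and 8.3.1 and footnote g stand, and Section 7.2 points to Table 1 for follow-up, so a careful site could keep the visit. That is a fair reading. It means the plan is unreconciled, not that it abolishes follow-up. It does not remove the problem, because a site that takes withdrawal at its word is also following the protocol.

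Some data survive withdrawal in any case. The early visit, if held, captures respiratory and survival status on that day. Section 8.3.1 keeps suspected-related serious events reportable even after the study ends. Appendix D has potential Hy's Law cases monitored until resolution or as long as medically indicated. Section 8.3.2 has unresolved events followed clinically, though without further case report form entries. A reader might infer that all later safety data are lost, and these provisions show otherwise.

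A reader might also infer that the rule discards the participants at highest risk, given the fatal reactivation in Section 2.3.1.3. The protocol does not rank risk in that way. The 9 reactivations among 4053 participants (0.22%) followed 43 to 582 days of therapy, and no HCV reactivation was reported. Dosing here is nominally 14 days, and the follow-up window reaches Day 43 only if the last dose is on Day 12 or later (12 + 31 = 43). The assessment would catch few such events. The likely loss is of general adverse event, laboratory and survival data.

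Two further arguments from Section 7.1 are weak. Its permissive verb introduces a general list that includes death and completed treatment, so it does not signal discretion about hepatitis. Its reminder that "Note that discontinuation from study intervention is NOT the same thing as a withdrawal from the study" separates two concepts, and Section 8.2.5.1.1 respects that by listing two steps. The conflict rests on the follow-up requirements.

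**Conclusion.** The point holds as an internal contradiction in the current text: study withdrawal is mandatory in two sections, and follow-up is required in four places with no matching exception. Read literally, the withdrawal rule costs up to 28 (±3) days of in-study safety data per affected participant, and the Day 14 and/or Day 28 status not yet reached, for people who remain in both analysis sets.

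The total is probably small: an expected 0.2 to 1.0 of 20 participants under the assumed 1% to 5%, fewer after the eligibility filters. The loss per person assumes that sites treat withdrawal as ending data collection, which the text permits but does not state. It does not threaten the study's main conclusions. It merits correction because the missing data would be avoidable, would fall on a primary objective and would arise without any withdrawal of consent.

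**What to change.** Reconcile the passages and leave the rule for stopping acalabrutinib as it is. In Sections 7.2 and 8.2.5.1.1, replace the instruction to withdraw from the study with a statement that these participants, unless they withdraw consent, remain in follow-up off drug for the Day 14, Day 28 and 28 (±3)-day safety assessments in Table 1. Hepatitis testing at follow-up should stay as Table 1 has it, when clinically indicated; no added testing is proposed.

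If the sponsor does intend data collection to end, Sections 4.4, 7.1 and 8.3.1 and footnote g each need an explicit exception, and the loss of safety data should be acknowledged.

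The cost is amendment wording in two sections. The assessments already exist, and footnote h recommends telemedicine for adverse events, concomitant medications and survival status at the safety follow-up, so the extra burden on sites and participants is slight.

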### **7.3 Lost to Follow-up**

A participant will be considered lost to follow-up if he/she repeatedly fails to return for scheduled visits and is unable to be contacted by the study site.

The following actions must be taken if a participant fails to return to the clinic for a required study visit:

- The site must attempt to contact the participant and reschedule the missed visit as soon as possible and counsel the participant on the importance of maintaining the assigned visit schedule and ascertain whether or not the participant wishes to and/or should continue in the study.
- Before a participant is deemed lost to follow up, the Investigator or designee must make every effort to regain contact with the participant (where possible, 3 telephone calls and, if necessary, a certified letter to the participant's last known mailing address or local equivalent methods). These contact attempts should be documented in the participant's medical record.
- Should the participant continue to be unreachable, he/she will be considered to have withdrawn from the study.

- Site personnel, or an independent third party, will attempt to collect the vital status of the participant within legal and ethical boundaries for all participants randomised, including those who did not get study intervention. Public sources may be searched for vital status information. If vital status is determined as deceased, this will be documented and the participant will not be considered lost to follow-up. Sponsor personnel will not be involved in any attempts to collect vital status information.

Discontinuation of specific sites or of the study as a whole are handled as part of Appendix A.

## 8 STUDY ASSESSMENTS AND PROCEDURES

- Study procedures and their timing are summarized in the SoA (Table 1). Protocol waivers or exemptions are not allowed.
- Immediate safety concerns should be discussed with the Sponsor immediately upon occurrence or awareness to determine if the participant should continue or discontinue study intervention.
- Adherence to the study design requirements, including those specified in the SoA (Table 1), is essential and required for study conduct.
- All screening evaluations must be completed and reviewed to confirm that potential participants meet all eligibility criteria. The Investigator will maintain a screening log to record details of all participants screened and to confirm eligibility or record reasons for screening failure, as applicable.
- Procedures conducted as part of the participant's routine clinical management (eg, blood count) and obtained before signing of the ICF may be utilized for screening or baseline purposes provided the procedures met the protocol-specified criteria and were performed within the time frame defined in the SoA (Table 1).

### 8.1 Efficacy and Clinical Assessments

#### 8.1.1 Efficacy Assessments

##### 8.1.1.1 Pulmonary Assessments to Evaluate Respiratory Failure

For the purpose of this study, **respiratory failure** is defined based on resource utilization of any of the following modalities:

- a) Endotracheal intubation and mechanical ventilation.
- b) Oxygen delivered by high-flow nasal cannula (heated, humidified, oxygen delivered via reinforced nasal cannula at flow rates > 20 L/min with fraction of delivered oxygen  $\geq 0.5$ ).
- c) Noninvasive positive pressure ventilation or continuous positive airway pressure.

d) Extracorporeal membrane oxygenation.

Arterial blood gases, and oxygen and ventilator use data will be captured to assess respiratory failure as described above.

If a participant requires oxygen supplementation, data will be recorded, including method of oxygen supplementation, maximum daily flow rate and FiO2.

If a participant requires mechanical ventilation, data will be recorded regarding whether ventilator weaning was attempted.

For participants on mechanical ventilation, the following ventilator settings will be recorded: tidal volume, FiO2, peak airway pressure over the last 24 hours, plateau pressure, positive end expiratory pressure, and respiratory rate. The data will be recorded qd, and the worst value of the day will be entered.

For participants on mechanical ventilation, an arterial blood gas (pH, PaO2, partial pressure of carbon dioxide, and FiO2 at the time the sample was obtained) will be recorded qd. If more than one value is obtained for the arterial blood gases, the value closest to 08:00 will be used.

Arterial blood gasses should be collected from participants if the sample is easily accessible and the procedure will not be painful to participants (ie, participant is in the ICU or has arterial port). All available data from the arterial blood gases should be entered into the database. If the collection of arterial blood gases is not clinically indicated, the test should not be performed.

Predicted body weight will be recorded on the ventilator eCRF for assessment of tidal volume.

Respiratory data will be used to evaluate the efficacy endpoints of proportion of participants alive and free of respiratory failure at Days 14 and 28.

### 8.1.1.2 Improvements on 9-point Category Ordinal Scale

For the purposes of this study, the condition of each potential participant in the study will be assessed using a 9-point category ordinal scale in Table 8. Assessments will be performed as described in the SoA (Table 1).

**Table 8 9-point Category Ordinal Scale**

Scale	Description
0 a	Uninfected, no clinical or virological evidence of infection
1	Ambulatory, no limitation of activities
2	Ambulatory, limitation of activities
3	Hospitalized – mild disease, no oxygen therapy

**Table 8 9-point Category Ordinal Scale**

Scale	Description
4	Hospitalized – mild disease, oxygen by mask or nasal prongs
5	Hospitalized – severe disease, non-invasive ventilation or high flow oxygen
6	Hospitalized – severe disease, intubation and mechanical ventilation
7	Hospitalized – severe disease, ventilation and additional organ support, such as pressors, renal replacement therapy, extracorporeal membrane oxygenation
8	Death

a Score of zero on 9-point category ordinal scale will not be evaluated in this study.

To be considered a “responder” to treatment with a target candidate, a participant needs to show an improvement of at least 2 points (from first dose) on this scale. Time to clinical improvement of 2 points will be assessed as a secondary endpoint.

## 8.1.2 Clinical Assessments

### 8.1.2.1 Modified Sequential Organ Failure Assessment Scores

A modified Sequential Organ Failure Assessment score will be calculated. For each of the following routine assessments, the worst value of the day will be recorded in the eCRF: PaO2/FiO2 (mmHg) or oxygen saturation/FiO2 (mmHg), platelet count, bilirubin, vasopressor use (µg/kg/min, mmHg), and creatinine ([or urine output]). For laboratory values, use last available (if within 48 hours). On days when laboratory results are unavailable, values will be extrapolated from the previously available values. Assessments will be performed as described in the SoA (Table 1).

## 8.2 Safety Assessments

Planned time points for all safety assessments are provided in the SoA (Table 1).

### 8.2.1 Medical History

Collect and record the participant’s relevant medical history through review of medical records and by interview. Concurrent medical signs and symptoms must be documented to establish baseline severities. Information on COVID-19 epidemiology will also be collected.

### 8.2.2 Physical Examinations and Chest Imaging

The screening physical examination will be symptom-directed and include height, weight and lung auscultation.

Per standard of care, chest imaging can be done by chest x-ray or CT scan with contrast, or any other appropriate means to confirm pneumonia prior to or upon hospitalization (within 7 days of enrollment). Post-treatment assessment will continue as clinically indicated.

Physical examination and chest imaging will be performed at time points specified in the SoA

(Table 1).

### **8.2.3 Vital Signs**

The vital signs to be collected are blood pressure, respiratory rate, pulse oximetry, heart rate, and body temperature. During screening, vital signs should be collected as close as possible to the dosing on Day 1. If more than one value is obtained for vital signs during screening, the value closest to the first dose of study intervention should be used. The oxygen-hemoglobin saturation of the blood will be assessed using standard pulse oximetry or by arterial blood gas for those participants who have an arterial blood gas obtained.

Vital signs will be performed at time points specified in the SoA (Table 1).

